17.1.2.1. PFS Censoring Rules (Set 1)

The PFS Censoring Rules (Set 1) will be used to manage missing data in the primary analysis of PFS. Under the Set 1 rules, PFS will be right-censored for subjects who meet one or more of the following conditions:

- Subjects with no post-baseline disease assessments (unless death occurred prior to the first scheduled assessment, in which case death will be considered a PFS event)
- Subjects who initiate subsequent anticancer therapy or intervention in the absence of documented progression
- Subjects who die or have disease progression after missing 2 or more consecutively scheduled disease assessment visits
- Subjects who are last known to be alive and progression-free on or before the data cut-off date

For such subjects, PFS will be right-censored according to the conventions described in Table E. These conventions are based on the May 2007 FDA Guidance for Industry “Clinical Trial Endpoints for the Approval of Cancer Drugs and Biologics”.

Table E. PFS Censoring Rules (Set 1): Date of Progression or Censoring

Situation	Date of Progression or Censoring	Outcome
Death before first scheduled disease assessment	Actual date of death	Progressed
Documented disease progression before first scheduled disease assessment	Actual date of disease assessment at which progression was noted	Progressed
Death or documented disease progression between 2 scheduled disease assessments	Actual date of death or actual date of first disease assessment showing documented disease progression, whichever occurs first	Progressed
Missed ≥ 2 consecutive disease assessments immediately prior to death or progression	Actual date of last non-missing disease assessment that is before the missed visits and prior to death and prior to documented disease progression	Censored
No death and no post-baseline disease assessments	Actual date of randomization	Censored
Non-protocol anticancer treatment started prior to death or prior to documentation of disease progression	Actual date of last non-missing disease assessment prior to start of non-protocol anticancer treatment	Censored
Alive and not progressed [1]	Actual date of last non-missing disease assessment	Censored

[1] Without death and without documentation of disease progression; includes subjects who may have discontinued from study prior to death and without documentation of disease progression.

17.1.2.2. PFS Censoring Rules (Set 2)

PFS Censoring Rules (Set 2) will be used for sensitivity analyses to address potential bias related to the violation of the assumption of non-informative censoring and missing disease assessments. The definition of a PFS event is expanded from the conventional definition of PFS specified in Set 1 rules to include subjects who discontinue protocol treatment, start non-protocol treatment prior to death or progression, or miss ≥ 2 consecutive disease assessments immediately prior to death or progression.

Under the Set 2 rules, the occurrence of a PFS event will be imputed (i.e. not be considered censored) under the following conditions:

- Discontinuation of treatment will be considered a failure of therapy. Therefore, subjects who discontinue therapy without death and without documented disease progression will be counted as an observed PFS event at the time of discontinuation.
- Patients for whom documentation of disease progression or death occurs immediately after ≥ 2 consecutive missed disease assessments will be considered to have had an observed PFS event on the date of the last disease assessment visit without documentation of disease progression prior to the missed visits.
- Patients who use any non-protocol anticancer treatment prior to documented disease progression will be considered to have had an observed PFS event on the start date of the new therapy.

PFS will be right-censored for subjects who meet one or more of the following conditions:

- Subjects with no post-baseline disease assessments unless death occurred prior to the first scheduled assessment (in which case death will be considered a PFS event).
- Subjects who are last known to be alive and progression-free on or before the data cut-off date.

Table F summarizes the handling of missing data and PFS determinations under the Censoring Rules (Set 2).

Table F. PFS Censoring Rules (Set 2): Date of Progression or Censoring

Situation	Date of Progression or Censoring	Outcome
Death before first scheduled disease assessment	Actual date of death	Progressed
Death or documented disease progression between 2 scheduled disease assessments	Actual date of death or actual date of first disease assessment showing documented disease progression, whichever occurs first	Progressed
Missed ≥ 2 consecutive disease assessments immediately prior to death or progression	Actual date of last non-missing disease assessment visit without a documented PFS event that is before the missed visits and before death or progression	Progressed
Treatment discontinuation prior to death and prior to documented disease progression	Actual date of the decision to discontinue treatment	Progressed
Non-protocol anticancer treatment started prior to death or prior to documented disease progression	Actual date of new treatment start	Progressed
No death and no post-baseline disease assessments	Actual date of randomization	Censored
Alive and no PFS* event	Actual date of last disease assessment	Censored

**The definition of PFS event under Set 2 rules includes the situations categorized as "Progressed" in the table.*

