3.5. SAMPLE SIZE JUSTIFICATION

For subjects with metastatic RCC who have progressed after at least 2 prior lines of therapy, a median PFS of 4 months is anticipated for the control agent. It is hypothesized that AGS-16C3F will improve median PFS in such subjects by 2 months (i.e., 4 vs 6 months). Under the assumption of exponential distribution of PFS, such an improvement corresponds to a hypothesized hazard ratio of 0.667. If this hypothesized hazard ratio is true, 110 PFS events provide 80% power to achieve a one-sided p-value of 0.1 or smaller. Such a result will be achieved when the observed hazard ratio is 0.783 or smaller; and the observed difference in median PFS is 1.1 months or larger (assuming observed median PFS for the control arm is 4 months). Assuming accrual of approximately 7 subjects per month for 18 months, 110 PFS events are projected 24 months after the date the first subject is randomized. Approximately 134 subjects may be enrolled to accommodate for up to 10% of subjects who may become lost to follow-up.

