17.1.2. MISSING DATA METHODS FOR PRIMARY EFFICACY VARIABLE

The analyses of PFS in this study are designed to be consistent with FDA guidance documents and the EMA scientific guidelines for analysis of PFS.

The EMA Guideline on the Evaluation of Anticancer Medicinal Products in Man (CHMP/EWP/205/95 Rev 34), Appendix 1, suggests that the primary analysis of PFS (defined as death or documented disease progression) should follow the ITT principles and be based on actual death dates and actual date of documentation of disease progression.

PFS Censoring Rules (Set 1) are designed to match this guidance except that subjects who receive non-protocol anticancer treatment without death or documentation of disease progression beforehand will be censored at the date of last disease assessment prior to the start of non-protocol anticancer treatment per May 2007 FDA Guidance for Industry “Clinical Trial Endpoints for the Approval of Cancer Drugs and Biologics”.

The guidelines also suggest that sensitivity analyses should be conducted to address important assumptions in the methods used, including the handling of deviations and missing data, censoring for subsequent anti-cancer treatment, non-radiological disease progression, and the handling of unscheduled evaluations. The PFS Censoring Rules (Sets 2, 3, 4) described in the sections below are designed to produce sensitivity analyses which address some of these concerns.

Under each set of censoring rules, if a subject fulfils the criteria for more than one situation, then the most conservative applicable outcome (“progressed”, followed by “censored”) will be assigned to the subject. Also, the shortest applicable time to event within the assigned outcome category will be used for the analysis.

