17.1.3. PRIMARY ANALYSIS OF PRIMARY EFFICACY VARIABLE

The primary objective of this study is to test the hypothesis that PFS is superior (longer) for subjects treated with AGS-16C3F than for subjects treated with axitinib.

The primary analysis of PFS based on the investigator's assessment of disease will be performed in accordance with the ITT principle in the FAS. All subjects who undergo randomization will be included in the primary analysis and grouped according to the treatment groups assigned by randomization. The Censoring Rules (Set 1) which are presented in Section 17.1.2.1 will be used to derive the event status and PFS times.

The difference between treatment groups will be tested using a stratified log rank test at a one-sided 0.1 significance level. The stratification factors will be the ECOG PS and the number of prior systemic RCC regimens, without any other covariate(s). If the direction of the difference between treatment arms favors AGS-16C3F, then the observed significance level (p-value) of the 1-sided test of superiority of AGS-16C3F will be calculated as $0.5 * p$ -value from a two-sided log-rank test (corresponding to a chi-squared test with d.f.=1). If the direction of the difference favors axitinib, then the observed significance level will be calculated as $(1 - (0.5 * p\text{-value from the two-sided log-rank test}))$.

Kaplan-Meier survival curves for the primary analysis variable will be produced, overall and by stratum. The following descriptive statistics will be reported in a table, overall and by stratum:

- Progression status:
 - Number and percent of subjects with observed disease progression per RECIST
 - Number and percent of subjects who died without disease progression beforehand
 - Number and percent of censored subjects
- Number and percent of censored subjects, by reason for censoring
- Estimated progression-free survival time (months), including the minimum, 25th percentile, 50th percentile (median), 75th percentile, and maximum. The 2-sided 95% CIs for the 25th, 50th, and 75th percentiles, calculated using Greenwood's formula for the standard error, will also be reported.

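### No PFS rule written for a death or progression after two or more missed scans uses its actual date: Sets 1, 3 and 4 censor it and Set 2 backdates it

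*SAP*

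**What the plan says.** SAP 17.1.2 cites a regulatory principle that PFS should rest on actual dates of death and documented progression. It then says: "PFS Censoring Rules (Set 1) are designed to match this guidance except that subjects who receive non-protocol anticancer treatment" are to be censored at their last prior assessment. No other exception is named.

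The Set 1 rules in 17.1.2.1 nevertheless list a further group to be right-censored: "Subjects who die or have disease progression after missing 2 or more consecutively scheduled disease assessment visits". Protocol Table 13 does the same.

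Set 2 (17.1.2.2) is the analysis meant to address informative censoring and missing assessments. Its text says that a subject with such a gap "will be considered to have had an observed PFS event on the date of the last disease assessment visit without documentation of disease progression" before the missed visits. Table F repeats this with outcome Progressed: "Actual date of last non-missing disease assessment visit without a documented PFS event that is before the missed visits".

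SAP 17.1.2 also has a tie-break for subjects who fit more than one row. An outcome of progressed outranks censored, and within the chosen outcome the shortest time is used.

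**The concern.** Protocol 7.4.1.2 and SAP 17.1.4 promise sensitivity analyses for bias from missed assessments. The natural check on Set 1's missed-scan censoring is to count the same events when they happened. No set is written to do that. Set 4 repeats Set 1's censoring, Set 3 also censors, and Set 2 goes past the actual date to the last negative scan. The per-protocol analysis (17.1.4.1) and the central-review PFS (17.2.2.1) reuse Set 1.

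The trial is open-label, so gaps in scanning could differ by arm. If they do, censoring moves the HR one way and backdating moves it past the actual-date value the other way. A difference between Sets 1 and 2 then cannot be read as a measure of informative censoring.

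**Working it through.** **1. Design figures, reproduced first.** SAP 3.5 states that "110 PFS events provide 80% power to achieve a one-sided p-value of 0.1 or smaller" and that "such an improvement corresponds to a hypothesized hazard ratio of 0.667"; medians are 4 and 6 months, allocation 1:1. Schoenfeld's formula gives 4(z₀.₁₀ + z₀.₂₀)²/(ln HR)² = 4(1.2816 + 0.8416)²/(0.4055)² = 109.7, so 110 events. The critical HR is exp(−1.2816 × 2/√110) = 0.783, and 4/0.783 − 4 = 1.1 months. All match the SAP, and nothing below changes them.

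**2. The missed-scan rows side by side.**

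| Set | Table | Outcome | Date used |
|---|---|---|---|
| 1 | E | Censored | last scan before the gap |
| 2 | F | Progressed | last scan before the gap |
| 3 | G | Censored | planned date of first missed scan |
| 4 | H | Censored | last scan before the gap |

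**3. Length of the backdating.** Scans are due every 8 weeks. Let the last negative scan be at week s and the missed ones at s + 8 and s + 16. The event then falls between s + 16 and s + 24. Set 2 dates it to s, which is 16 to 24 weeks (3.7 to 5.5 months) early, against assumed medians of 4 and 6 months.

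**4. Precedence.** A death or progression after a gap that falls between two scheduled scans also fits the row in Tables E and H that counts an event on its actual date. Read literally, the tie-break selects that row in Sets 1 and 4 (and, for deaths, in Set 3). The explicit text says such subjects are right-censored. In Set 2 both rows are Progressed and the shorter time wins, so backdating stands on either reading.

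**5. Illustration for deaths with a known date.** The missed-scan share is an assumption, because the documents give none. Simulation: 67 per arm, exponential PFS with control median 4 months, uniform accrual over 18 months, cut-off at 24 months, 8-week scans, unstratified Cox model, 1,500 trials per row. The last column applies only Set 2's missed-scan rule, not the whole of Set 2. Under a true HR of 0.667:

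| Late deaths after a gap (axitinib / AGS-16C3F) | Actual date | Censored | Backdated |
|---|---|---|---|
| 0% / 0% | 0.665 | 0.665 | 0.665 |
| 10% / 10% | 0.663 | 0.658 | 0.661 |
| 0% / 10% | 0.675 | 0.645 | 0.714 |
| 5% / 15% | 0.676 | 0.642 | 0.716 |
| 10% / 0% | 0.657 | 0.684 | 0.618 |

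Ten percent of one arm is about 7 subjects (0.10 × 67). In the 0%/10% row, going from censored to actual date moves the HR by 0.675 − 0.645 = 0.030. Going from censored to backdated moves it by 0.714 − 0.645 = 0.069, more than twice as far. The mean backdating was about 4.5 months.

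Under a true HR of 1 with 10% in the axitinib arm only, the one-sided 0.10 rejection rate is 0.126 on actual dates, 0.092 censored and 0.211 backdated. The Monte Carlo standard error is about 0.01: √(0.211 × 0.789/1,500). The 0.126 itself sits above the no-gap 0.107, because exact death dates precede the scan dates assigned to the other events.

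**6. Counter-check for progressions.** Suppose instead that 10% of the AGS-16C3F arm truly progressed by the first missed scan and were documented two scans later. Full scanning gives 0.662, actual documentation date 0.625, censored 0.601 and backdated 0.666. Here backdating is the closest.

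**The case against.** The strongest reply is that Sets 1 and 2 can be read as opposite bounds. Set 2 openly imputes events. A progression found after a gap happened at an unknown time between the last negative scan and the detecting scan, so the last negative scan is a legitimate lower bound and the detection date is late. Step 6 bears this out, and this part stands. A reader might infer that the actual-date version is unbiased throughout; that is not so for progressions. It does not rescue backdating for deaths, whose dates are known.

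Other stronger readings also go too far:

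- **That no analysis could ever use the actual date.** The 17.1.2 tie-break, taken literally, would use it in Sets 1 and 4. The defensible statement is that no row written for this situation does, and that the SAP contradicts itself.
- **That Set 2 dates a never-scanned subject at or before randomization.** The 17.1.2.2 text right-censors subjects with no post-baseline scan unless they die before the first scheduled one. For a late death, Table F's missed-scan row points back to baseline, while its no-assessment row covers only subjects who have not died. That is a conflict to resolve, not a settled rule.
- **That the figures above are Set 2 results.** Set 2 also counts treatment discontinuation and new therapy as events, so the column isolates only one of its rules.
- **That power or the 110-event design suffers.** Neither depends on Set 2.

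The SAP partly covers the ground elsewhere: off-schedule scans by arm (16.2), reasons for censoring (17.1.3) and censoring times by arm (17.1.6). These would reveal an imbalance but not its effect on the HR.

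**Conclusion.** The point holds in this form: for events after two or more missed scans the plan offers censoring or backdating, with no rule written for the actual date, so the promised missed-scan check lacks its most direct version. For deaths the backdating is plainly wrong as a date, by about 16 to 24 weeks with exactly two missed scans. The list of departures in 17.1.2 is incomplete, and its tie-break conflicts with the censoring rows. That conflict reaches the primary analysis, because the Main Analysis cut-off is set on PFS events counted under Set 1 (SAP 4.2).

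The effect on the HR is conditional. With gaps in one arm only (10%), backdating moves it about 0.04 from the actual-date value and censoring about 0.03 the other way. With balanced gaps the change is at most 0.005. These figures rest on assumed gap rates, exponential times and deaths with known dates. They indicate direction and rough size and do not predict the trial's result. This should be corrected, but it does not undermine the primary design.

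**What to change.** 1. Add one sensitivity analysis identical to Set 1 except that a death or documented progression after two or more missed scans is an event on its actual date. Editing Set 2 alone would not isolate the effect, because its discontinuation and new-therapy events would still be mixed in.
2. In Set 2, keep backdating only for progressions, labelled as a worst-case bound, and date deaths on the day they occurred. For progressions, read the actual-date and backdated versions as bounds.
3. In 17.1.2, declare both departures of Set 1 from actual dates. State that the missed-scan row prevails over the tie-break in Sets 1 and 4, as the explicit right-censoring text and Protocol Table 13 require; say the same for deaths in Set 3.
4. In Table F, state how a subject with no post-baseline scan who dies late is handled, and align the text with it.
5. Report the number of missed-scan events by arm with the censoring reasons.

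The cost is SAP wording, one derivation and one extra analysis. The dates are already collected and the 110-event design is unchanged.

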17.1.2.3. PFS Censoring Rules (Set 3)

The PFS Censoring Rules (Set 3) are based on Table B (PFS 2 – uniform progressions and assessment dates) of the May 2007 FDA Guidance for Industry “Clinical Trial Endpoints for the Approval of Cancer Drugs and Biologics”. Set 3 rules are designed to correct for potential bias due to any differences in the follow-up schedules for disease assessments, including unscheduled visits. These alternative censoring rules will be used for sensitivity analyses of the PFS.

Under Set 3 rules, an observed PFS event is defined as documented disease progression or death due to any cause. The occurrence of a PFS event will be imputed to the date of the scheduled disease assessment time. Accordingly, the dates of observed events will be adjusted as follows:

- If disease progression is documented between 2 scheduled disease assessments, the planned date of the later scheduled assessment will be assigned as the date of progression.
- In the event of death, the date of the endpoint will not be adjusted.

- If the response at a scheduled time (X) is classified as Indeterminate (IND) or Not Assessed (NA) and at the next scheduled timepoint (X+1) the best response is PD, then the planned date of the first timepoint (X) will be used as the uncensored date of progression.
- Censoring will be similar to Set 1, except that the planned dates of scheduled assessments will be used for the censored values.

Table G summarizes the handling of missing data and PFS determination under the Censoring Rules (Set 3).

Table G. PFS Censoring Rules (Set 3): Uniform Progression and Assessment Dates

Situation	Date of Progression or Censoring	Outcome
Death before first scheduled disease assessment	Actual date of death	Progressed
Death or documented disease progression at a scheduled disease assessment	Actual date of death or planned date of the scheduled disease assessment, whichever occurs first	Progressed
Death or documented disease progression between scheduled disease assessments	Actual date of death or planned date of next subsequent scheduled disease assessment after the documented disease progression, whichever occurs first	Progressed
A disease assessment of “indeterminate” or “not assessed” at Visit X, followed by documented disease progression at Visit X+1	Planned date of scheduled disease assessment at Visit X	Progressed
Non-protocol anticancer treatment started prior to death or without prior documentation of disease progression	Planned date of last non-missing scheduled disease assessment prior to start of non-protocol anticancer treatment.	Censored
No death and no post-baseline disease assessments	Actual date of randomization	Censored
Missed ≥ 2 consecutive disease assessments immediately prior to death or progression	Planned date of the first of ≥ 2 missed disease assessment visits prior to death and prior to documented disease progression	Censored
Alive and no PFS event*	Planned date of last non-missing scheduled disease assessment	Censored

*The definition of PFS event under Set 3 rules includes the situations categorized as “Progressed” in the table.

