**Table 13 Date of Progression or Censoring for PFS**

Situation	Date of Progression or Censoring	Outcome
Death or disease progression between planned disease assessments	Date of death or first disease assessment showing disease progression, whichever occurs first	Progressed
Death before first planned disease assessment	Date of death	Progressed
No post-baseline disease assessments	Date of randomization	Censored
Non-protocol anti-cancer treatment started before death or without documentation of disease progression beforehand	Date of last disease assessment prior to start of non-protocol anti-cancer treatment	Censored
Death or disease progression after missing 2 or more consecutively scheduled disease assessments	Date of last disease assessment visit without documentation of disease progression that is before the missed visit	Censored
Alive and without documentation of disease progression	Date of last disease assessment	Censored

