6.6. VISIT WINDOWING CONVENTIONS

Subjects in both treatment arms will have disease assessments every 8 weeks (± 7 days), counting from first dose or first infusion, irrespective of any treatment delay. The Schedule of Assessments (Protocol Section V) provides additional information about the procedures and assessments that are to be completed during each visit or Cycle.

The EDC-specified visit designations, and/or Cycle and Cycle Day designations for AGS-16C3F subjects, will be used for listings and for any summaries by visit or timepoint.

If visit windowing is determined to be required for any analysis, the upper limit of each analysis window will be the protocol-specified upper limit of the “acceptable” window for each assessment. The lower limit of the next consecutive window will be set to the following day. Within each window, the assessment closest to the target day and time will be selected for analysis, unless otherwise specified. Other assessments within the window will be treated as unscheduled or PRN assessments. This strategy will help to keep the results aligned with any event-based presentations that may be produced.

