17.1.2.4. PFS Censoring Rules (Set 4)

The PFS Censoring Rules (Set 4) are designed to address possible limitations of the scientific methods used for documentation of disease progression by including symptomatic or non-radiological disease progression as an observed PFS event.

Set 4 rules will be used for sensitivity analyses. Under Set 4 rules, an observed PFS event is defined as clinical (i.e., symptomatic or non-radiological) disease progression, documented disease progression, or death due to any cause. Subjects who do not experience clinical or documented disease progression or death during the analysis period will be censored.

PFS will be right-censored for subjects who meet one or more of the following conditions:

- Subjects with no post-baseline disease assessments (unless death occurred prior to the first scheduled assessment, in which case death will be considered a PFS event)
- Subjects who initiate subsequent anticancer therapy or intervention in the absence of documented progression
- Subjects who die or have disease progression immediately progression immediately after missing 2 or more consecutively scheduled disease assessment visits
- Subjects who are last known to be alive and progression-free on or before the data cut-off date

For such subjects, PFS will be right-censored according to the conventions described in Table H.H These conventions are based on the May 2007 FDA Guidance for Industry “Clinical Trial Endpoints for the Approval of Cancer Drugs and Biologics”.

Table H. PFS Censoring Rules (Set 4): Date of Progression or Censoring

Situation	Date of Progression or Censoring	Outcome
Death before first scheduled disease assessment	Actual date of death	Progressed
Death, documented disease progression or clinical progression between 2 scheduled disease assessments	The earliest of: (1) actual date of death, (2) actual date of first disease assessment showing clinical disease progression, (3) actual date of first disease assessment showing documented disease progression	Progressed
Missed ≥ 2 consecutive disease assessments immediately prior to a PFS event	Actual date of last non-missing disease assessment that is prior to the missed visits and prior to any PFS event	Censored
No death and no post-baseline disease assessments	Actual date of randomization	Censored

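### Set 3 sensitivity analysis: Table G censors at the first missed scan, eight weeks later than the Set 3 text implies

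*SAP*

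**What the plan says.** SAP Section 17.1.2.3 states the Set 3 rule in text and again in Table G.

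- **Text:** "Censoring will be similar to Set 1, except that the planned dates of scheduled assessments will be used for the censored values". Planned for actual dates is the only exception named.
- **Table G**, two or more missed assessments immediately before death or progression: censored at the "Planned date of the first of ≥ 2 missed disease assessment visits prior to death and prior to documented disease progression".

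The same situation elsewhere:

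- **Set 1** (SAP 17.1.2.1, Table E): "Actual date of last non-missing disease assessment that is before the missed visits and prior to death and prior to documented disease progression".
- **Protocol Table 13:** "Date of last disease assessment visit without documentation of disease progression that is before the missed visit".
- **Set 4** (SAP 17.1.2.4, Table H): "Actual date of last non-missing disease assessment that is prior to the missed visits and prior to any PFS event".
- **Set 2** (SAP 17.1.2.2, Table F) counts an event instead of censoring, but dates it to the last assessment before the gap.

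Within Table G, subjects alive without an event are censored at the "Planned date of last non-missing scheduled disease assessment", and the new-anticancer-treatment row uses the same anchor. The fourth censoring row, for no death and no post-baseline assessment, uses the randomization date. Neither Section 17.1.2.3 nor the log of changes in Section 3.3 explains the different anchor; the log describes Sets 2 to 4 only as added detail.

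**The concern.** Replacing an actual date by a planned date keeps the same visit and tidies its date. Table G does something else: it moves the censoring date to a later visit, at which the subject was not assessed. A programmer working from the text and one working from the table would build different datasets.

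Set 3 is there to correct for differences between the arms in the timing of assessments. A rule that credits unassessed time to subjects who miss scans helps the arm with more missed scans, which is the kind of imbalance Set 3 is meant to neutralise. It also blurs the comparison of Set 3 with Set 1: that comparison should show the effect of uniform dating, but would carry an undeclared 8-week shift as well.

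**Working it through.** **1. The plan's own figure.** Inputs from SAP 3.5: HR 0.667, one-sided alpha 0.10, power 80%, 1:1 allocation.

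Events = 4 × (1.2816 + 0.8416)² / (ln 0.667)² = 18.03 / 0.1640 = 110. This reproduces the SAP. The critical HR is exp(−2 × 1.2816 / √110) = 0.783, also as stated. The Set 3 rule enters neither figure.

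**2. Gap between the two dates.** SAP 6.6 schedules scans every 8 weeks (56 days), ±7 days. If the last scan seen is planned for day 56k, the first missed one is planned for day 56(k+1).

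| Last scan seen | Following the text | Following Table G | Difference |
|---|---|---|---|
| Week 8 | day 56 | day 112 | 56 days |
| Week 16 | day 112 | day 168 | 56 days |
| Week 24 | day 168 | day 224 | 56 days |

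For example, a subject scanned at week 16 misses weeks 24 and 32 and progresses at week 40. Table G censors at week 24; the text gives week 16.

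- In months: 56 / 365.25 × 12 = 1.84. This is 1.84/4 = 46% of the assumed control median and 1.84/6 = 31% of the assumed AGS-16C3F median.
- From the actual scan date, with the ±7-day window: 49 to 63 days, or 7 to 9 weeks.
- Chance of an event in 1.84 months under the plan's exponential model: 1 − 2^(−1.84/4) = 27% (control) and 1 − 2^(−1.84/6) = 19% (AGS-16C3F).

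**3. Effect on the hazard ratio (illustrative).** The documents give no missed-scan rate, so the shares below are assumptions.

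Simulation: 67 subjects per arm, exponential PFS with medians 4 and 6 months, 8-week scans, uniform accrual over 18 months, cut-off at month 27 (three months after the plan's projection), 400 runs. The Cox model was unstratified with Breslow ties; the SAP uses a stratified model with Efron ties. The share applies to subjects whose progression is detected at the third scheduled scan or later; in those affected, the two preceding scans are missed. The censoring row is taken to govern.

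| Share affected, control / AGS-16C3F | HR, Table G | HR, text rule | Shift |
|---|---|---|---|
| 10% / 10% | 0.690 | 0.688 | 0.002 |
| 20% / 20% | 0.692 | 0.690 | 0.002 |
| 0 / 10% | 0.665 | 0.673 | −0.008 |
| 0 / 20% | 0.651 | 0.667 | −0.016 |
| 0 / 30% | 0.636 | 0.660 | −0.024 |
| 20% / 0 | 0.741 | 0.720 | +0.021 |

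Compare within rows only: both rules use the same simulated data in a row, but each row is a fresh set of runs. The sign shows that the gain goes to the arm that misses more scans.

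**4. Overlap with another row.** Table G also has a row for a visit X that is indeterminate or not assessed, followed by progression at X+1: progressed, dated to the planned date of X. A subject who misses X−1 and X and progresses at X+1 fits both that row and the censoring row. SAP 17.1.2 says that progressed outranks censored when several situations apply. Read literally, this subject is an event at X and the disputed date is never used. The simulated subjects follow exactly this pattern, so the shifts in step 3 arise only if the censoring row takes precedence.

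**The case against.** **The anchor may be deliberate.** Section 17.1.2.3 says Set 3 is based on a table in the 2007 FDA guidance, which cannot be consulted here, and the text says similar to Set 1, not identical. Set 3 also assigns planned dates with no scan behind them elsewhere: progression between visits moves forward to the next planned date, and progression after a visit not assessed moves back to that visit. This stands as a reason not to call the cell a certain slip. It does not remove the conflict, because the one exception the text names does not cover a change of visit.

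**The effect is small.** This stands too. Balanced missed scans leave the hazard ratio almost unchanged, and the one-arm rates are assumptions. To qualify after a week-8 scan, a subject must also be event-free to week 24 (5.52 months): 2^(−5.52/4) = 38% of control and 2^(−5.52/6) = 53% of AGS-16C3F subjects under the plan's model. A reader might infer a larger effect from crude person-time. With about 52 events at a 6-month median, person-time is 52 × 6 / ln 2 = 450 months; if 15% of 67 subjects gain 1.84 months each, 18.5 months are added and the crude hazard falls by 18.5 / 468.5 = 3.9%. The documents do not support that figure: the 15% has no source, and the planned analysis is a stratified log-rank test and Cox model, not a crude rate.

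**An imbalance would be visible.** The SAP tabulates off-schedule and missing scans by arm (16.2), reports reasons for censoring (17.1.3) and compares censoring times by arm (17.1.6). That helps to detect the problem; it does not settle which date to program.

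**Conclusion.** The contradiction is real and can be seen from the SAP alone. Table G dates this group exactly 8 weeks later than the text of its own section implies, and differs from the anchor used for the same situation in Sets 1, 2 and 4 and in the protocol. The 8 weeks follow from the visit schedule and need no assumption. The effect on the hazard ratio rests on assumed rates of missed scans and on the censoring row governing: about 0.002 if balanced, about 0.01 to 0.02 if 10–30% of one arm is affected.

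Two stronger readings are not supported. A reader might infer that the primary result is at risk; it is not, since the primary analysis and the data cut-off use Set 1, and sample size and power do not involve Set 3. A reader might also infer that the rule favours AGS-16C3F; it favours whichever arm misses more scans, and the documents do not show which that would be. This is a minor correction to a sensitivity analysis, worth making because it is nearly free.

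**What to change.** 1. In Table G, change the date for two or more consecutive missed assessments to "Planned date of last non-missing scheduled disease assessment" followed by the words *before the missed visits*; the outcome stays Censored.
2. State that, when two or more consecutive visits are missed, this row takes precedence over the row for a visit not assessed and then followed by progression. Changing the cell alone leaves the general rule in 17.1.2, under which that subject would count as progressed.
3. If the first-missed-visit anchor was intended, keep the cell, but amend the sentence in 17.1.2.3 to name this second departure from Set 1 and justify it. Item 2 is needed either way.

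The cost is one table cell and one sentence in the SAP, plus the matching line in the analysis dataset specification. No data collection, sample size or primary analysis is affected.
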